13.5.3 Laboratory Assessments

Laboratory data will be summarized by the type of laboratory test and will be presented for each scheduled visit stratified by treatment group and overall. Shift tables of the number of patients with

low/normal/high (or normal/abnormal, as appropriate) values at each scheduled post-baseline visit compared to the low/normal/high (or normal/abnormal, as appropriate) categorization at baseline will be provided by treatment group and overall. For the visits of the extension phase, additionally the shifts from baseline of the extension (Day 0 Treatment Period 7) will be provided. Summary tables of actual values and changes from baseline will be provided for each continuous laboratory parameter at each scheduled visit by treatment group and overall. For the visits of the extension phase, additionally the change from baseline of the extension will be provided.

13.5.4 Vital Signs

Summary tables of the actual values and changes from baseline will be provided for each vital sign parameter at each scheduled visit by treatment group and overall. For the visits of the extension phase, additionally the change from baseline of the extension will be provided.

13.5.5 ECG

For each 12-lead ECG variable the actual value and the change from baseline will be summarized for the scheduled visits by treatment group and overall. For the visits of the extension phase, additionally the change from baseline of the extension will be provided. A shift table of the number and percentage of patients with normal and abnormal, and clinically significant abnormal values at each scheduled post-baseline visit compared to the normal / abnormal /clinically significant abnormal categorization at baseline will be provided by treatment group for the overall interpretation. For the visits of the extension phase, additionally the shifts from baseline of the extension (Day 0 Treatment Period 7) will be provided.

Frequency tables of abnormal clinically significant evaluations as well as the number and percentage of patients with noteworthy QTcF/QTcB values (> 450 , > 480 and > 500 ms) and of patients with noteworthy QTcF/QTcB changes from baseline (≥ 30 but < 60 ; ≥ 60 ms) will be provided. For the extension phase additionally the number and percentage of patients with noteworthy QTcF/QTcB changes from baseline of the extension (Day 0 Treatment Period 7) will be provided

14. DIRECT ACCESS TO SOURCE DATA/DOCUMENTS

Individual patient medical information obtained as a result of this study is considered confidential and disclosure to third parties other than those noted below is prohibited. Upon the patient's permission, medical information may be given to the patient's personal physician or to other appropriate medical personnel responsible for the patient's welfare. Data generated as a result of this study must be made available for inspection upon request by representatives of the US FDA, national and local health authorities, the Sponsor or its representatives, and by the IRB/IEC (or equivalent).

15. QUALITY CONTROL AND QUALITY ASSURANCE

15.1 Study Monitoring

In accordance with applicable regulations, ICH-GCP and procedures covering the study, a monitor will contact the site prior to the patient enrollment to review the protocol and data collection procedures with site staff. In addition, the monitor will periodically contact the site, including conducting on-site visits at an appropriate frequency to ensure data quality and to ensure the safety and rights of patients are being protected.

The investigator agrees to allow the monitor direct access to all relevant documents and to allocate his/her time and the time of his/her staff to the monitor to discuss findings and any relevant issues.

15.2 Audits and Inspections

To ensure compliance with Good Clinical Practices and all applicable regulatory requirements, quality assurance audits may occur during the study or after the study is complete. Authorized representatives of the Sponsor, the CRO conducting the study, a regulatory authority, an IRB/IEC may visit the site to perform audits or inspections to examine all study-related activities and documents to determine whether these activities were conducted, and data were recorded, analyzed, and accurately reported according to the protocol, ICH-GCP, and any applicable regulatory requirements.

If an audit or inspection occurs, the Investigator and institution agree to allow the auditor/inspector direct access to all relevant documents and to allocate his/her time and the time of his/her staff to the auditor/inspector to discuss findings and any relevant issues. The Investigator should contact the Sponsor immediately if contacted by a regulatory agency about an inspection.

15.3 Protocol Modifications

The initial protocol as well as all protocol amendments must be signed and dated by the Investigator and approved by the IRB/IEC prior to implementation of the original protocol and any amendment. The Principal Investigator must submit all protocol modifications to the IRB/IEC, as applicable for specific Investigators, or applicable local regulatory authority. The Sponsor or designee will submit protocol modifications to the FDA as needed.

Departures from the protocol will be determined as allowable on a case-by-case basis or in event of an emergency involving patient safety. The Investigator or other physician in attendance must contact the Medical Monitor as soon as possible to discuss the circumstances of the emergency. The Medical Monitor, in concurrence with the Investigator, will decide whether the patient should continue to participate in the study. All protocol deviations and the reason for such deviations must be noted on the source document and in the CRF, and reported to the IRB/IEC as appropriate.

16. ETHICS AND GOOD CLINICAL PRACTICE COMPLIANCE

Good Clinical Practice (GCP) is an international ethical and scientific quality standard for designing, conducting, recording, and reporting trials that involve human patients. Compliance with this standard provides public assurance that the rights, safety, and well-being of study patients are protected, consistent with the principles that have their origin in the Declaration of Helsinki ([World Medical Association 2013](#)), and that the clinical trial data are credible.

The study will be conducted under a US IND and all applicable US FDA and local laws and regulations and Good Clinical Practice Guidelines. The Investigator agrees to conduct the study in compliance with the current version of US Food Drug & Cosmetic Act, Section 21 CFR, Part 312, Subpart D (Responsibilities of Sponsor and Investigators), part 50 (Protection of Human Subjects), part 56 (Institutional Review Boards), the principles of the Declaration of Helsinki, and with the laws and regulations of the country in which the research is conducted in order to afford the greatest protection to the individual. The Investigator must fully adhere to the principles outlined in the “Guideline for Good Clinical Practice” International Conference on Harmonisation (ICH) Tripartite Guideline and, for studies conducted in the EU/European Economic Area (EEA) countries, the Investigator will ensure compliance with the EU Clinical Trial Directive [2001/20/EC].

This study will be conducted in full compliance with the Institutional Review Board (IRB) / Independent Ethics Committee (IEC) regulations in 21 CFR 56 and applicable local regulatory guidance, in accordance with ICH-GCP. IRB/IEC approval for the investigation must be obtained before the study is initiated. Initial IRB/IEC approval, and all materials approved by the IRB/IEC for this study including the patient consent form and recruitment materials must be maintained by the Investigator and made available for inspection.

17. DATA HANDLING AND RECORDKEEPING**17.1 Data Management****17.1.1 Case Report Forms**

Data for this study will be recorded via an EDC system using eCRFs. It will be transcribed by the site from the paper source documents onto the eCRF.

The information collected on eCRFs must be identical to the corresponding information appearing in original source documents. There are no exceptions to this rule. In general, source documentation will be found in a chart maintained by qualified medical personnel in a hospital, clinic, or physician's office. (The eCRF is not considered as source data for this trial).

Accurate and reliable data collection will be assured by verification and cross check of the eCRFs against the Investigator's records by the study monitor (source document verification), and the maintenance of a drug dispensing log by the Investigator.

As a matter of regulations, the Investigator is responsible for the accuracy and authenticity of all clinical and laboratory data entered onto eCRFs. Prior to submission, each completed eCRF must be reviewed for accuracy by the Investigator, corrected as necessary, and then approved and e-signed. The Investigator's e-signature serves to attest that the information contained on the eCRFs has been reviewed by the Investigator and is true and accurate.

The eCRFs should be completed by the Investigator or a qualified designee from the site as soon as the data are available. Instructions for the completion of eCRFs will be provided.

The eCRFs will be considered complete when all missing, incorrect, and/or inconsistent data have been accounted for.

17.1.2 Retention of Records

An Investigator must maintain adequate records to include the disposition of the study drug(s) and adequate and accurate source documentation that record all observations and other data pertinent to the investigation on each patient in the study. These records are to include the case report forms (CRFs), source documentation, and supporting data, including, for example, signed and dated informed consent forms and medical records (including progress notes by the physician and/or other qualified medical personnel, the patient's hospital and clinic chart[s], and the nurses' notes).

The FDA (21 CFR §312.62[c]) states that the Investigator shall retain the required records:

- a. For a period of 2 years following the date a marketing application is approved for the drug for the indication for which it is being investigated; or
- b. If no application is to be filed or if the marketing application is not approved for such indication, until 2 years after the investigation is discontinued and the FDA is notified.

If neither a) nor b) applies, then the Investigator shall retain the required records for a minimum of 15 years after the completion or discontinuation of the study.

For sites outside the US, the Investigator must comply with US FDA regulations and with the record retention policies of the relevant national and local health authorities. The Investigator must obtain the Sponsor's written permission before disposing of any records.

If the Investigator retires, relocates, or for any reason withdraws from the study, then the study records may be transferred to an acceptable person or institution with the written approval of the Sponsor.

18. REPORTING STUDY RESULTS AND PUBLICATION POLICY

Following analysis of the data and upon request by the Investigator, the Sponsor will supply a listing of site-specific treatment assignments, tabulated data, and statistical analysis, as appropriate. A summary of the study results will be provided to each Investigator following its release by the Sponsor. The Investigator will acknowledge receipt of any data listings or study results.

Guidelines concerning publication of the results of this clinical study are contained within the formal Clinical Study Agreement associated with this protocol.

20. APPENDICES

APPENDIX A SCHEDULE OF ASSESSMENTS: DOUBLE-BLIND TREATMENT PHASE

Assessment	Scr. - 45 d to D0 (Pre-dose) ³	Double-Blind Treatment Phase														EOS ¹	ET	
		TP1 ²		TP2 ²		TP3 ²		TP4 ²		TP5 ²		TP6 ²						
		D0	D21 ⁴	D0 ⁵	D7 ⁴	D14 ⁴	D21 ⁴	D28 ^{5,25}										
Informed Consent	X																	
Demographics	X																	
Inclusion/Exclusion	X																	
Medical History	X																	
Chest X-Ray	X															X	X	
Multi-energy CT ⁶	X							X								X	X	
Physical Examinations	X ⁷	X ⁸		X ⁸		X ⁸		X ⁸		X ⁸		X ⁸				X ⁷	X ⁷	
Vital Signs	X	X ⁹		X ⁹		X ⁹		X ⁹		X ⁹		X ⁹		X	X		X	
Weight and Height ¹⁰	X		X		X		X		X		X			X	X		X	
12-Lead ECG	X															X	X	
Screening Labs ¹¹	X																	
COVID-19 Testing	X																	
Urine Pregnancy Test	X																	
Washout: ULTs	X ¹³	Patients will abstain from ULT use after the ULT washout period																
Document ULTs Discontinued	X																	
Dispense Premedication: Gout Flare and Infusion Reaction ¹²	X		X		X		X		X		X				X			
Premedication: Gout Flare	X ¹⁴																	
Randomization	X ¹⁵ <-----> X ¹⁵																	
Premedication: Infusion Reaction		X ¹⁶		X ¹⁶		X ¹⁶		X ¹⁶		X ¹⁶		X ¹⁶						
Safety Labs: Chemistry ¹⁷	X	X	X		X		X		X		X				X	X	X	
Safety Labs: Hematology ¹⁸	X	X	X		X		X		X		X			X	X		X	
Safety Labs: Coagulation ¹⁹	X	X	X		X		X		X		X			X	X		X	
Safety Labs: Lipids ²⁰	X	X	X		X		X		X		X			X	X		X	
Safety Labs: eGFR ¹⁷	X	X	X		X		X		X		X			X	X		X	
Blood Sample for Anti-Pegadricase ²¹		X	X	X	X	X	X	X	X	X	X	X			X	X	X	
Blood Sample for nAbs ²¹		X	X	X	X	X	X	X	X	X	X	X			X	X	X	
Blood Sample for Anti-Pegadricase POC Validation ²¹		X	X	X	X	X	X	X	X	X	X	X			X	X	X	
Blood Sample for Anti-Uricase ²¹		X	X	X	X	X	X	X	X	X	X	X			X	X	X	
Blood Sample for Biomarkers ⁶		X		X		X							X	X		X	X	

Blood Sample for Multiomic Markers		X		X		X		X		X	X			X		X
Blood Sample for HLA Typing			X													
Blood Sample for T Cell Analysis		X								X	X			X		X

Appendix A Schedule of Assessments, continued

Assessment	Scr. - 45 d to D0 (Pre-dose) ³	Double-Blind Treatment Phase														EOS¹	ET	
		TP1 ²		TP2 ²		TP3 ²		TP4 ²		TP5 ²		TP6 ²						
		D0	D21 ⁴	D0 ⁵	D7 ⁴	D14 ⁴	D21 ⁴	D28 ^{5,25}										
Tophus Assessment/Photography	X							X								X	X	
Gout Flare Assessment ²²	X	X	X	X	X	X	X	X	X	X	X	X	X	X	X	X	X	
Gout Flare Weekly Diary		Continuously on Weekly Basis ²⁴															X	
Joint Assessment (tenderness, swelling)		X						X								X	X	
Health Questionnaires ²³		X						X								X	X	
Collect Sample for sUA	X	Refer to Schedule of Assessments (Appendix B) for sUA Sample Collection during Treatment Phase															X	
PD/Uricase Activity Assessment		Refer to Schedule of Assessments (Appendix B) for PD/Uricase Activity Assessments during Treatment Phase															X	
Study Drug Administration		Refer to Schedule of Assessments in Appendix B for Study Drug Administration during the Treatment Phase																
Infusion Reaction Follow-up		Refer to Section 12.2.1.5																
Concomitant Medications / Procedures		Continuously														X	X	
AE Collection		Continuously														X	X	
SAE Collection		Continuously														X	X	

1. Phone call at 30 (+4) days after the last study drug infusion for assessment of concomitant medications/procedures, AEs, and SAEs.
2. Visit window at Day 21 of each Treatment Period is +2/-1 days; visit window at Day 7 and Day 14 of Treatment Period 6 is +2/-1 days; visit window at Day 28 of Treatment Period 6 is +3/-4 days.
3. Visit window is -2 days.
4. Assessments at this visit are permitted to be performed remotely (inclusive of collecting applicable lab draws and assessments per protocol visit windows).
5. Study drug dosing to occur 28 days from the previous dose with a window of -4 days to +3 day of the intended dosing day. If a protocol deviation occurs where a patient is not able to be dosed within the dosing day window, for example in the case of COVID-19 restrictions temporarily preventing dosing, the current treatment period will be extended up to a maximum of 90 days without skipping doses for patients with a Day 21 visit sUA value \leq 1.0 mg/dL during Treatment Period 1 or \leq 6.0 mg/dL during Treatment Periods 2-11 in the D21 visit window or subsequent up to the rescheduled dosing visit. If this protocol deviation occurs such that the patient was unable to be dosed within the dosing day window for the Treatment Period 7 Day 0 dose, then the Treatment Period 6 Day 28 visit should still occur 28 days (+3/-4 days) after the Treatment Period 6 dose or as close to the visit window as possible to collect the final primary endpoint SUA sample. In this specific instance, the dosing day Treatment Period 7 Day 0 should then occur as soon as possible afterward up to a maximum of 90 days from the preceding dose.
6. Assessment performed at select sites only
7. Full physical exam
8. Directed physical exam

9. Assess vital signs on Day 0 at Time 0 (pre-dose), within + 5 minutes after completion of infusion of the first component of study drug, and 1 hour (+ 5 minutes) after completion of infusion of the second component of study drug.
10. Height measured once during Screening only.
11. Screening labs to include: calcium, total complement, hemoglobin-A1c (HbA1c), hepatitis C antibody, hepatitis B surface antigen, human immunodeficiency virus 1/2 (HIV1/2), urinalysis, glucose-6-phosphate dehydrogenase (G6PD)
12. Dispense gout flare medication at Screening and as needed during the study. Dispense infusion reaction medication at Screening and at Day 21 of Treatment Periods 1-11.
13. Begin at least 7 days prior to Day 0 of Treatment Period 1.
14. Begin at least 7 days prior to Day 0 of Treatment Period 1.
15. Randomization is permitted at any time between Day -7 to Day 0 (prior to SEL-212 administration).
16. Premedication to minimize potential infusion reactions: oral antihistamines at 12 (\pm 2) hours and 2 (\pm 1) hours and IV steroids at 1 (\pm 0.5) hours prior to study drug.
17. Chemistry labs to include: Alkaline phosphatase, alanine aminotransferase (ALT), aspartate aminotransferase (AST), Total Bilirubin, blood urea nitrogen (BUN), Creatinine, UACR, eGFR, Fibrinogen, Glucose (fasting), Electrolytes (sodium, potassium, chloride, bi-carbonate, phosphate and magnesium).
18. Hematology labs to include: white blood cells (WBC) count with differential, Red blood cell (RBC) count, Hematocrit (Hct), Hemoglobin (Hgb), Platelet (Plt) count, and absolute neutrophil count (Abneu)
19. Coagulation labs to include: prothrombin time (PT), activated partial thromboplastin time (aPTT), international normalized ratio (INR)
20. Fasting lipid labs to include: total cholesterol, high density lipoprotein (HDL), low density lipoprotein (LDL), triglycerides
21. Collect sample prior to study drug dosing
22. Gout flares assessed based on validated gout flare definition ([Gaffo 2018](#))
23. Refer to [Section 11.3](#) for Health Questionnaires.
24. Start gout flare diary at Day 0 of Treatment Period 1.
25. Treatment Period 6 Day 28 assessments will be used for Treatment Period 7 Day 0 assessments. Do not repeat sample collection on Treatment Period 7 Day 0.

Abbreviations: CT: computed tomography; D (d): day; ECG: electrocardiogram; eGFR: estimated glomerular filtration rate; EOS: end of study; ET: early termination; h: hour; nAbs: neutralizing antibodies; PD: pharmacodynamic; RCTC: Rheumatology Common Toxicity Criteria; Scr: Screening Phase; sUA: serum uric acid; TP: treatment period; UACR: urine-albumin-creatinine ratio; ULT: urate lowering therapy

APPENDIX B SCHEDULE OF ASSESSMENTS: DOSING, SUA, AND URICASE ACTIVITY DURING THE DOUBLE-BLIND TREATMENT PHASE

Assessments	Day Timepoint	Treatment Periods: 1, 2, 3, 4, and 5				Treatment Period 6							
		D0 ¹				D0 ¹				D7 ²	D14 ²	D21 ²	D28 ³
		0h	~1.5h	~3.5h	~4.5h		0h	~1.5h	~3.5	~4.5h			
Premedicate: Infusion Reaction		X ⁴					X						
Blood Sample Uricase Activity		X ⁵			X ⁶	X	X ⁵			X ⁶	X	X	X
Blood Sample: sUA		X ⁵			X ⁶	X	X ⁵			X ⁶	X	X	X
Study Drug Infusion (Component 1) ⁷		X-----X ⁸					X-----X ⁸						
Study Drug Infusion (Component 2) ⁹			X ⁸ -----X					X ⁸ -----X					

1. Study drug dosing to occur 28 days from the previous dose with a window of -4 days to +3 day of the intended dosing day.
2. Assessments at this visit are permitted to be performed remotely (inclusive of collecting applicable lab draws and assessments per protocol visit windows).
3. Treatment Period 6 only. Treatment Period 6 Day 28 assessment will be used for Treatment Period 7 Day 0 pre-dose assessment. Do not repeat sample collection on Treatment Period 7 Day 0.
4. Premedication to minimize potential infusion reactions: oral antihistamines at 12 (± 2) hours and 2 (± 1) hours and IV steroids at 1 (± 0.5) hours prior to study drug.
5. Obtain sample prior to study drug infusion.
6. Obtain sample 1 hour (+15/-0 min) after completion of infusion of Component 2. If a patient is withdrawn from study drug, the post-dose uricase activity and post-dose sUA samples do not need to be collected.
7. Component 1 will be SEL-110.36 at 0.1 mg/kg for patients randomized to treatment with SEL-212A and SEL-110.36 at 0.15 mg/kg for patients randomized to SEL-212B or will be placebo for patients randomized to placebo.
8. Before starting infusion with Component 2, a period of up to approximately 30 minutes is permitted after completion of infusion of Component 1.
9. Component 2 will be SEL-037 for patients randomized to treatment with either SEL-212A or to SEL-212B or will be placebo for patients randomized to placebo.

PHASE 3 STUDY: SEL-212/301
VERSION: 6.1

EFFECTIVE DATE

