12.1.7 Chest X-ray

Chest X-rays (CXR) will be performed according to the schedule described in [Appendix A](#) and [Appendix C](#). [Post-baseline CXRs will be taken](#) to assess for presence of or changes in interstitial lung disease (ILD) compared to baseline CXR.

12.1.8 **Laboratory Assessments**

All laboratory assessment will be conducted according to the schedule described in [Appendix A](#) and [Appendix C](#). Procedures for processing samples are included in the Study Operations Manual.

12.1.8.1 **Hematology**

Hematology assessments will include white blood cells (WBC) count with differential, red blood cell (RBC) count, hematocrit (Hct), hemoglobin (Hgb), and platelet (Plt) count.

12.1.8.2 **Blood Chemistry**

Clinical chemistry assessments will include alkaline phosphatase, alanine aminotransferase (ALT), aspartate aminotransferase (AST), total bilirubin, blood urea nitrogen (BUN), creatinine, fibrinogen, glucose (fasting), and electrolytes (sodium, potassium, chloride, bicarbonate, phosphate, and magnesium), and urine for urine-albumin-creatinine ratio (UACR). If the UACR cannot be calculated due to the microalbumin analysis being below the limit of quantification for the analytical method (eg. <12 mg/dL), the low microalbumin can be used as a surrogate for an acceptable UACR.

12.1.8.3 **Glomerular Filtration Rate (GFR)**

Estimated glomerular filtration rate (eGFR) will be calculated according to the Study Operations Manual.

12.1.8.4 **Lipids**

Fasting lipid assessments will include total cholesterol, high-density lipoprotein (HDL), low-density lipoprotein (LDL), and triglycerides.

12.1.8.5 **Coagulation**

Coagulation assessments will include prothrombin time (PT), activated partial thromboplastin time (aPTT), international normalized ratio (INR).

12.1.8.6 **Antibody Assessments**

Blood samples will be collected for assessment of antibody development to pegadricase and uricase, and for neutralizing antibodies and anti-pegadricase point of service validation. All blood samples for assessment of antibody development are required to be collected prior to study drug dosing. Antibody samples collected after the screening period will be assessed only in patients in active treatment arms.

12.1.8.7 **COVID-19 Testing**

Patients with COVID-19 infection can experience a range of clinical manifestations, from no symptoms to critical illness.

Screening Visit:

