### **7.2. Key Definitions**

Baseline (of the study) is defined as the last non-missing value prior to the start date and time of the study drug. For Health questionnaires (including HAQ-DI, SF-36, and PGA), gout flare assessment, tender joint assessment and swollen joint assessment, if no assessment is available prior to the start time of the study drug, assessments post the start of study drug but on the date of first study drug administration may be considered as Baseline. Tophus status at baseline in the study will be based on IRT. Baseline of the extension period is defined as the assessment prior to first dosing on Day 0 of Treatment Period 7.

Day 0 of Treatment Period 1 is defined as the first date of study drug administration.

Overall study day will be calculated as date of event/collection – first dose date of the study.

Study day within each treatment period will be calculated as date of event/collection – first dose date at each treatment period to be consistent with protocol which defines the day of dosing in each treatment period as day 0.

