### **9.1. Assessment of sUA Time Curve and Summaries**

The sUA time curve with assessments at Day 0, pre-treatment (0 h), Day 0, post-treatment (4.5 h), Day 7, Day 14, Day 21 and Day 28 in TP6 will be used to estimate the proportion of time that the sUA level is below 6 mg/dL by Day 28. Based on the serum samples collected during TP6 an estimate of the time with sUA < 6 mg/dL can be determined by connecting each two neighboring data points with a straight line. If the sUA time curve goes above 6 mg/dL the linear interpolation method will be used to estimate the point in time at which the sUA time curve intercepts the line between the last sUA value < 6 mg/dL and the first value  $\geq$  6 mg/dL. The proportion of time that the sUA level is < 6 mg/dL will be computed by taking the ratio between the time during which the sUA level remains < 6 mg/dL (if necessary, using the linear interpolation method) and the entire time interval within TP6 by Day 28. Actual times will be plotted on the time curve, but only the interpolation of actual times up to Day 28 will be used. For example, if a patient had their Day 28 assessment on Day 30 then a straight line will connect Day 30 and their previous assessment, but the percentage of time the time curve is < 6 mg/dL will be derived only up to Day 28. If a point at Day 28 is not available on the curve (possibly due to an extension of TP6 for reasons such as presenting mild-moderate COVID-19 symptoms), then the next available assessment between Day 28 and up to, and including Day 0, pre-treatment (0 h) in TP7 will be used to interpolate the curve up to Day 28. This can include the use of unscheduled sUA assessments. For example, if a patient is missing their Day 28 assessment, and the next assessment is at Day 0, pre-treatment (0 h) in TP7 then this additional timepoint will be plotted as the time in days from Day 0 in TP6. A straight line will be connected between this and the last assessment in TP6 and the percentage of time the time curve is < 6 mg/dL will be derived up to Day 28. Further, if the same patient has an unscheduled visit on Day 40 of TP6 (e.g., once their mild-moderate COVID-19 resolve) then the straight line will be connected between this and their previous assessment in TP6 prior to Day 28 (as Day 40 is now the next available assessment between Day 28 and up to, and including Day 0, pre-treatment (0 h) in TP7) and the percentage of time the time curve is < 6 mg/dL will again be derived up to Day 28. If there are no such assessments available, but the use of unscheduled assessments allows the extension of the time curve from the last scheduled assessment prior to Day 28 then these can also be used. For example if a patient has all scheduled assessments during TP6 up to Day 21, with no assessments on or after Day 28, up to and including Day 0, pre-treatment in TP7, but has an unscheduled assessment on Day 25 then the percentage of time with sUA level < 6 mg/dL for TP6 would be taken to be the percentage of time the sUA levels were < 6 mg/dL from Day 0 to Day 25. If only 2 or fewer assessments are available (allowing for the use of assessments after Day 28 up to, and including Day 0, pre-treatment (0 h) of TP7, and further unscheduled assessments prior to Day 28), and the first and last attended assessments are less than 7 actual days apart, then the response evaluation of TP6 will be missing. For a patient to be considered a responder in TP6, the proportion of time that the SUA level is < 6 mg/dL (i.e., percentage of nonhyperuricemic time) during TP 6 by Day 28 (or last available assessment prior to Day 28 if no

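### When the TP7 dose is delayed, the schedule carries TP6 Day 28 values over as TP7 pre-dose values, so pre-dose sUA, uricase activity and antibody results can be 59 to 66 days old at dosing

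*Protocol*

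**What the plan says.** Two sets of instructions meet at the start of the extension.

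**Timing when the TP7 dose is late.** Protocol 7.4.1.1 and Appendix A footnote 5 separate the two visits. The end-of-period visit stays put: "the Treatment Period 6 Day 28 visit should still occur 28 days (+3/-4 days) after the Treatment Period 6 dose", or as close to that window as possible. The dose may move: "Treatment Period 7 Day 0 should then occur as soon as possible afterward up to a maximum of 90 days from the preceding dose".

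**Sampling.** Appendix A footnote 25 and Appendix C footnote 18 state: "Treatment Period 6 Day 28 assessments will be used for Treatment Period 7 Day 0 assessments". Appendix B footnote 3 and Appendix D footnote 2 are narrower: "Treatment Period 6 Day 28 assessment will be used for Treatment Period 7 Day 0 pre-dose assessment". All four add "Do not repeat sample collection on Treatment Period 7 Day 0". SAP Tables A to D repeat them. None mentions a delayed dose.

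**Use of the values.** SAP 7.2 states: "Baseline of the extension period is defined as the assessment prior to first dosing on Day 0 of Treatment Period 7". SAP 9.3.5 gives D0 TP7 as the extension baseline in its opening text and for joints, questionnaires and the provider global assessment, but names D28 TP6 for sUA. For antibodies, Protocol 12.1.8.6 says: "All blood samples for assessment of antibody development are required to be collected prior to study drug dosing".

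**The concern.** The carry-over suits the ordinary case, in which Day 28 and the next dose share a visit. The delay rule creates a case in which they do not, and the footnotes were not adjusted to it. A site that follows them literally gives the TP7 dose with no scheduled pre-dose sUA, uricase-activity or antibody sample since Day 28.

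The TP7 pre-dose value is then a measurement from another point in the dosing cycle. sUA below 6 mg/dL before the TP7 dose would be scored from Day 28. For antibodies, the next scheduled sample is TP7 Day 21, so a rise during the gap could not be told apart from a rise after re-dosing. Protocol 7.7 lists possible re-treatment after a gap of more than a month among the potential benefits. These few patients could inform that claim, and the dosing-day sample is the one they lack.

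**Working it through.** The plan states no figure for the age of the carried-over value, so there is none to reproduce.

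**Inputs**
- Latest TP7 dose: day 90 after the TP6 dose (Protocol 7.4.1.1; Appendix A footnote 5).
- TP6 Day 28 visit: day 28, window +3/-4, so day 24 to day 31 (same places).
- Ordinary dosing window: also day 24 to day 31 (Appendix A footnote 5).

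**Formula:** age at dosing = day of TP7 dose − day of TP6 Day 28 sample.

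| Day 28 sample drawn on | Longest age at TP7 dose |
|---|---|
| Day 24 | 90 − 24 = 66 days (9.4 weeks) |
| Day 28 | 90 − 28 = 62 days (8.9 weeks) |
| Day 31 | 90 − 31 = 59 days (8.4 weeks) |

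With dosing in window, the age is at most 31 − 24 = 7 days. The rule therefore does little harm unless the dose is delayed.

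**Comparison with other periods.** Appendices B and D schedule a 0 h sUA and uricase-activity sample on Day 0 of every period, and Appendices A and C schedule antibody samples on every Day 0. Only TP7 has a footnote replacing the draw with an earlier one. For a delayed dose in any other period, the age of these three measurements is 0 days.

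**Where the values are used**
- Pre-dose sUA below 6 mg/dL in the extension (Protocol 6.2.4; SAP 9.3.5).
- Pre-treatment antibody levels by extension period (Protocol 6.2.4; SAP 9.3.5).
- Change from extension baseline (SAP 7.2 and 9.3.5). SAP 10.4 counts antibodies among the laboratory tests summarized as change from D0 TP7.

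Protocol 6.2 and SAP 9.3.5 make the extension efficacy summaries descriptive.

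**The case against.** The strongest reply is that the footnotes bar a repeat, not all sampling, and that other text leaves room for a fresh value. Much of this stands, and it limits the point.

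- **Post-dose sampling is untouched.** Appendix D confines the carry-over to the pre-dose assessment and keeps the sUA and uricase samples at about 4.5 h on TP7 Day 0. A reader might infer that all TP7 Day 0 sampling is forbidden; it is not.
- **SAP 9.1 does not contradict the footnotes.** A reader might see a conflict because, when no Day 28 point exists, "then the next available assessment between Day 28 and up to, and including Day 0, pre-treatment (0 h) in TP7 will be used" to complete the TP6 curve. In that case a TP7 Day 0 draw repeats nothing. Protocol 13.4.1 says the same.
- **Safety laboratories are not a TP7 problem.** Appendix C schedules none on Day 0 of TP8 to TP12. A dose delayed to day 90 there leaves Day 21 results 90 − 21 = 69 days old, against 62 days here.
- **A fresher value is allowed.** Appendix A footnote 5 accepts an sUA taken up to the rescheduled visit, and SAP 7.4 admits unscheduled values to baseline derivation. But no text requires an sUA, uricase-activity or antibody draw on the delayed dosing day, and the footnotes discourage one.
- **For sUA, D28 TP6 is a named reference.** Because SAP 9.3.5 specifies it, a Day 28 sUA baseline is not in itself an error. What remains is that SAP 9.3.5 and SAP 7.2 point to days that differ in a delayed patient.

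None of these removes the case in which Day 28 was drawn, the dose came much later, and no pre-dose sample was taken.

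**Conclusion.** The point holds as a gap between the delay rule and the sampling footnotes. Its size is an age of up to 59 to 66 days for scheduled TP7 pre-dose sUA, uricase-activity and antibody values, assuming that the Day 28 visit falls in its window, the delay runs to the full 90 days, and no optional sample is drawn. Shorter delays give proportionately fresher values.

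The consequence is small: no confirmatory result changes when Day 28 is drawn. Two stronger readings go beyond the documents:

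- **An error in mg/dL for the extension baseline.** The 7 mg/dL at entry is a minimum for eligibility, not a ceiling for untreated sUA, and the plan gives no course of sUA during a gap after six doses.
- **A number of affected patients.** No delay rate is given, and patients who met the stopping rule receive no TP7 dose, so the whole active group is not the right base.

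It is still worth correcting, because the remedy is cheap and gives TP7 the dosing-day samples that every other period has.

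**What to change.** 1. Reword Appendix A footnote 25, Appendix B footnote 3, Appendix C footnote 18 and Appendix D footnote 2, and the matching notes in SAP Tables A to D. TP6 Day 28 values should serve as TP7 Day 0 values only when both fall on the same visit. If the TP7 dose is given on a later day, the scheduled pre-dose sUA, uricase-activity and antibody samples should be drawn on that day.
2. Reconcile SAP 7.2 with SAP 9.3.5 so that there is one extension baseline: the last value on or before the actual TP7 dose. Keep Day 28 values for the TP6 endpoints. For variables not re-measured on the delayed dosing day, such as joint counts and questionnaires, this definition still returns the Day 28 value; the SAP should say so.

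The cost is footnote wording, a short SAP edit, and one extra pre-dose draw in patients with a delayed TP7 dose, at a visit they already attend. No change to any dosing or stopping rule is proposed.
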